Methodology

Study design and Patient selection

Patients with a history of migraine diagnosis who presented at the Research Polyclinic of Karabuk University Training and Research Hospital for wet-cupping therapy in the period May 2016-January 2018 were included in the study. Patients were excluded if they had a history of head and neck surgery, a diagnosis of sinusitis, a diagnosis of fibromyalgia and inflammatory disease (rheumatism, infection etc.), were pregnant, had a diagnosis of cancer, bleeding disorder and widespread skin disease, malignant hypertension or any other disease which could cause headache. The diagnosis of migraine was confirmed by an experienced neurologist and the migraine type was determined. The medical treatments of the patients were reviewed and MIDAS was applied to determine the baseline score. In addition to the medical treatment, WCT was applied once a month, 3 times (Day 0, 30, 60). At the end of the 3rd month patients were allocated into two parallel arms. They were randomly assigned to the intervention group or control group in a double blind manner by the sealed opaque envelope technique. Intervention group continued WCT whereas patients in the control group discontinued the treatment. MIDAS was applied again at the end of the 6th and 12th months to both of the groups. Disability values in the 6th and 12th months were evaluated with MIDAS between those who continued treatment (Group 1) and those who did not (Group 2). Approval for the study was granted by Turgut Ozal University Ethics Committee, with number 99950669/236, dated 30.06.2014. Study design, application procedures and any possible side effects were explained to the study participants and informed consents obtained. All procedures performed in studies involving human participants were in accordance with the ethical standards of the institutional and/or national research committee and with the 1964 Helsinki declaration and its later amendments or comparable ethical standards.

MIDAS

The migraine disability score is a scale evaluating disability and loss associated with migraine. It consists of 7 questions, the 1st, 3rd and 5th of which evaluate the days lost from school, work, housework or leisure activities because of headaches in the last 3 months. The 2nd and 4th questions evaluate the number of additional days lost from work or housework in the last 3 months due to a reduction in productivity (defined as at least a 50% reduction in productivity). An additional two questions (MIDAS A and B) evaluate the frequency of headaches and the severity of the headaches using a visual analog scale (VAS), but these are not added to the total MIDAS score. The total MIDAS points are obtained from the total of the first 5 questions. Total points of 0-5 = 1st degree (very little or no restriction), 6-10 points =2nd degree (mild or occasional restriction), 11-20 points = 3rd degree (moderate level of restriction), and 21 + points = 4th degree (severe restriction).

Wet cupping technique

CT was applied using plastic disposable vacuum cups on the back in the 5 areas of C7 cervical spine (DU14 acupoint), T2-4 lateral spine bilaterally (BL41-42 acupoint) and T6-8 lateral spine bilaterally (BL44-46), which are the recommended sites for headache (12). The cupping technique procedure was conducted in five phases:

1. Primary suction; the cups are placed on the selected area with a manual suction pump which draws air out from inside the cups. The cups are left attached to the skin for 5 minutes. The skin and subcutaneous tissue swells.

2. Area disinfection; the swollen areas are wiped with sterile gauze after disinfection with povidone iodine.

3. Scarification; Superficial incisions (20-30 gauge), 5 mm length and 1-2 mm depth, are made on the skin with a sterile, number 11 surgical blade.

4. Bloodletting and secondary suction; the cups which had been previously removed are placed again on the scarified areas using a manual pump in the same way as described above. Blood leaks from the capillary vessels of the skin and subcutaneous tissue and fills the cups, which are left in place for 15 minutes.

5. Removing and dressing; the cups full of blood are removed after 15 mins. The areas of application are wiped with sterile gauze and then a dressing is applied.

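### The exclusion list covers a diagnosed bleeding disorder but no anticoagulant drug, so read literally a patient already on a therapeutic anticoagulant is eligible for scarification and bloodletting (minor patient-safety point)

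*Protocol*

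**What the plan says.** Under Methodology, Study design and Patient selection, patients are excluded for earlier head and neck surgery, for a series of diagnoses, and for pregnancy. The part that bears on bleeding excludes those who "were pregnant, had a diagnosis of cancer, bleeding disorder and widespread skin disease, malignant hypertension or any other disease which could cause headache". The sentence contains no medication criterion.

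At entry, "The medical treatments of the patients were reviewed and MIDAS was applied to determine the baseline score". What the review of treatments is for, and what it may lead to, is not stated.

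Every patient is then treated before allocation: "In addition to the medical treatment, WCT was applied once a month, 3 times (Day 0, 30, 60". Allocation follows at the end of the third month, after which "Intervention group continued WCT whereas patients in the control group discontinued the treatment". The interval and the end of the continued cupping are not given.

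Under Wet cupping technique, the first two phases are suction and skin preparation, in which "the swollen areas are wiped with sterile gauze after disinfection with povidone iodine". The third is the cut: "Scarification; Superficial incisions (20-30 gauge), 5 mm length and 1-2 mm depth, are made on the skin with a sterile, number 11 surgical blade". The cups are then reapplied for 15 minutes and fill with blood.

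**The concern.** By excluding bleeding disorders, the protocol already accepts that impaired clotting is a reason not to perform this procedure. A therapeutic anticoagulant impairs clotting by design, yet the list covers the disease and not the drug. The information needed to apply such a rule is apparently collected at entry, but no rule uses it.

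What is at stake is patient safety. The procedure draws blood deliberately, is repeated, and is given to everyone before randomisation. Whether an anticoagulated patient is cut should be settled by the protocol and not by how a particular clinician understands the term bleeding disorder. The comparison of MIDAS between the groups is not at issue.

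**Working it through.** The protocol gives no figure on this point, so there is none to reproduce. The check sets the relevant statements side by side and asks whether any of them would stop a patient who is on a therapeutic anticoagulant at entry.

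1. **Exclusion list.** It consists of a surgical history, diagnoses, pregnancy and a closing catch-all. The bleeding item stands among the diagnoses. The catch-all concerns diseases that may cause headache, so it does not reach a drug that raises bleeding risk. A patient anticoagulated for a listed condition is excluded by that condition; a patient anticoagulated for an unlisted one is not.

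2. **Entry medication review.** Treatments are reviewed, but no exclusion, dose hold, washout or coagulation test follows.

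3. **Background treatment.** Cupping is added to medical treatment. This most naturally means migraine treatment. That other drugs continue is an inference: nothing requires them to be stopped.

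4. **Technique.** Two phases come before the cut, suction and disinfection. Neither includes a check of medication or bleeding tendency.

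5. **Consent.** The protocol says that "Study design, application procedures and any possible side effects were explained to the study participants and informed consents obtained". Telling patients about risks does not decide who is eligible.

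None of the five closes the gap.

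**Exposure of such a patient**

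- Run-in sessions: Days 0, 30 and 60, which is 3. The patient is anticoagulated from entry, so Day 0 counts, and the exposure is 3 of 3.
- All 3 precede allocation, so assignment to the control group avoids none of them.
- Group 1 has additional sessions. The documents give neither their interval nor their last date, so the number is left unstated here.

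**Excess harm.** This would need the share of patients on anticoagulants and the bleeding rates with and without them. The protocol gives none of these, so no estimate is made.

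**The case against.** The strongest case against is that this is a silence and not an error. Nothing in the protocol says that anticoagulated patients may be cupped, and no two statements conflict. The list is loosely written, and a clinician could fairly read bleeding disorder to include a drug-induced tendency. Patients came to a hospital clinic and their treatments were reviewed, so clinical judgement at entry is a reasonable expectation. The consent pages are not available and may carry a warning about such drugs. The incisions are 1-2 mm deep, the blood is capillary, and no figure in the protocol shows that anticoagulant use is dangerous here.

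Part of this stands. The looser reading is possible, the cuts are shallow, and the step from a bleeding disorder to an anticoagulant rests on general medical knowledge. These points keep the matter minor. They do not remove it: the exclusion list is a stated rule, and followed as written it admits the patient. A consent warning would not be an eligibility criterion. Eligibility is also protocol content, so a statistical analysis plan that is not shown would not be expected to supply it.

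A reader might infer more than the text supports:

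- **That anticoagulated patients were enrolled or harmed.** The protocol shows neither.
- **That a total number of exposed sessions can be given for Group 1.** It cannot. "MIDAS was applied again at the end of the 6th and 12th months to both of the groups" fixes when disability was measured, not how often or how long cupping continued. Any total would rest on an assumed interval and an assumed end.
- **That questions at every session, a check before the envelope is opened, and stopping rules are needed.** Those concern patients who start an anticoagulant after entry, which is a different and weaker point. The gap in the entry wording does not require them.

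**Conclusion.** The point holds as a minor, cheap improvement to patient safety. The protocol excludes a diagnosed bleeding disorder, names no anticoagulant and attaches no eligibility consequence to its own medication review. Read literally, a patient already on a therapeutic anticoagulant is eligible for all 3 run-in sessions and, in Group 1, for an unstated number more.

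This rests on two conditions: that bleeding disorder is read as a diagnosis, which is how the sentence places it, and that the patient takes the drug for a condition not otherwise excluded. No excess bleeding is shown or estimated, and no sample size, estimate or test is affected.

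**What to change.** Reword the exclusion to: bleeding disorder or current therapeutic anticoagulant treatment. State that it is applied at the entry medication review, which already takes place.

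If the sponsor also means to exclude antiplatelet drugs, it should say so in the same phrase; the protocol gives no basis for deciding that here.

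The protocol is written in the past tense. For patients already enrolled, the useful step is a sentence stating how those on anticoagulants were handled. The rewording serves any continued or repeated use of the protocol.

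The cost is one phrase and its link to an existing step, with no new visit or test. The downside is that a few patients become ineligible; how many cannot be said from the document.

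### The protocol calls the assignment double blind, but sealed envelopes only conceal allocation, and patients who continue or stop wet cupping know their arm when they answer MIDAS at months 6 and 12

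*Protocol*

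**What the plan says.** The protocol's Methodology, under 'Study design and Patient selection', describes a common run-in for all patients: "In addition to the medical treatment, WCT was applied once a month, 3 times (Day 0, 30, 60"). Randomisation follows at the end of the third month: "They were randomly assigned to the intervention group or control group in a double blind manner by the sealed opaque envelope technique". The next sentence gives the treatment contrast: "Intervention group continued WCT whereas patients in the control group discontinued the treatment". Follow-up is the same in both arms: "MIDAS was applied again at the end of the 6th and 12th months to both of the groups". On what participants were told, it says: "Study design, application procedures and any possible side effects were explained to the study participants and informed consents obtained".

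The 'MIDAS' section says that three of the five scored questions "evaluate the days lost from school, work, housework or leisure activities because of headaches in the last 3 months". The other two scored questions count further days on which productivity fell by at least half, over the same period. It adds: "An additional two questions (MIDAS A and B) evaluate the frequency of headaches and the severity of the headaches"; these two do not enter the total.

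The 'Wet cupping technique' section describes suction, superficial incisions with a surgical blade, a second suction that draws blood, and a dressing. At the last step, "the cups full of blood are removed after 15 mins".

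**The concern.** Allocation concealment and blinding are different protections. Concealment stops whoever enrols a patient from foreseeing the next assignment, and so guards against selection at entry. Blinding stops knowledge of the treatment from influencing behaviour and reporting after entry. The protocol names a mechanism for the first and claims the second.

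The only between-group comparison described is MIDAS at months 6 and 12. If patients know whether they kept the treatment, their expectations can affect how many lost or low-productivity days they report. They came to the clinic for wet cupping, so it is plausible that they held expectations about it. A reader who trusts the double-blind label could set this aside and credit the whole difference to cupping.

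**Working it through.** The protocol states no sample size, effect size or standard deviation that bears on this point, so there is no figure of its own to reproduce. The check compares the blinding claim with the design and then counts the exposure.

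**Step 1. What the named mechanism does.** The sealed opaque envelope is the only mechanism given. It acts up to the moment of opening. No sham procedure, blinded assessor or other masking is described.

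**Step 2. Can patients and operators be unaware of the arm?**

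| Element | What the protocol describes | Consequence |
|---|---|---|
| Contrast after month 3 | one arm continues cupping, the other discontinues | the arms differ in whether a procedure takes place |
| Nature of the procedure | suction, incisions, blood-filled cups, dressing | evident to the patient and to the operator |
| Earlier experience | three sessions (Day 0, 30, 60) in every patient before randomisation | the patient recognises its presence or absence |
| Information given | study design and procedures explained to participants | the patient can tell what continuing or stopping means |
| Background care | cupping is added to medical treatment, and nothing says that treatment stopped | cupping remains the visible difference |

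Patients and operators therefore know the arm no later than the first session given or omitted after month 3.

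**Step 3. Who supplies the outcome?** MIDAS has 5 scored + 2 unscored = 7 questions. The protocol does not use the term self-reported. The content makes the patient the source: days lost, days at half productivity or less, headache frequency, and severity on a visual analogue scale. An interviewer who did not know the arm would still be recording answers from a patient who did.

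**Step 4. How much of the outcome period is exposed?** The 3-month recall is stated for the scored questions. The window runs from (assessment month − 3) to the assessment month, and randomisation is at the end of month 3.

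- Month 6: 6 − 3 = 3, so the window covers months 4 to 6. Months before randomisation = max(0, 3 − 3) = 0 of 3.
- Month 12: 12 − 3 = 9, so the window covers months 10 to 12. Months before randomisation = max(0, 3 − 9) = 0 of 3.
- Together: 3 + 3 = 6 of 6 recalled months fall after randomisation.

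This is a count of exposure, not an estimate of bias. It shows only that no part of either follow-up score comes from a period before the arms diverged.

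**The case against.** The strongest reply is grammatical. The double-blind phrase modifies the act of assignment; the protocol never calls the treatment period, the MIDAS assessment or the follow-up comparison blinded. On that reading the authors have misnamed allocation concealment, for which sealed opaque envelopes are a proper tool. The reading is possible, and nothing here disputes the concealment. It does not rescue the term, which readers take to mean that patients and staff or assessors are masked to treatment. The comparison is unblinded on either reading.

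Four further objections stand in part:

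- No bias has been demonstrated. That is correct: the fault is a false label on a patient-answered comparison, and the seriousness rests on that.
- The month count would look the same in most trials that assess outcome after randomisation. That is also correct, and it is offered only as exposure. The 3-month window is not stated for the two unscored questions.
- Patient reporting is inferred from item content. It is, but the content leaves little room for another source.
- Silence on whether the MIDAS administrator or the analyst was blinded is no error, since an analysis plan that is not shown may cover it. It is a request for clarification and does not carry the point. Nor could such a plan make continuing versus stopping a masked comparison.

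**Conclusion.** The concern holds. The protocol attributes to the trial a property that its own next sentence rules out. Allocation may well have been concealed, but patients and the staff giving cupping were not blinded, and the month 6 and month 12 MIDAS comparison is in effect open-label.

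The direction and size of any resulting bias are unknown and cannot be derived from the document. The conclusion rests on two assumptions: that no sham was given to the arm that stopped, since none is described, and that patients answered the MIDAS questions themselves, directly or through an interviewer. The correction is necessary because the label bears on how the only described between-group comparison is interpreted.

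**What to change.** In 'Study design and Patient selection', replace the double-blind phrase with wording such as: *with allocation concealed by sealed opaque envelopes; patients and the staff giving wet cupping were not blinded*. The sponsor should confirm whether this also holds for other treating staff, such as those managing the medical treatment.

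As a clarification, state whether the person administering MIDAS or the analyst was blinded.

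Interpret the between-arm MIDAS difference as the effect of continuing versus stopping wet cupping, including the effect of knowing the allocation, and acknowledge possible expectation and reporting bias.

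The change is one of wording and interpretation: no procedure, sample size or analysis alters. The cost is a slightly more modest conclusion, because the effect of cupping cannot be separated from knowledge of the arm.

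### No MIDAS score is scheduled at randomisation: the only earlier score predates all three run-in cupping sessions

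*Protocol*

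**What the plan says.** The schedule is in the Protocol, Methodology, under Study design and Patient selection. At entry, "The medical treatments of the patients were reviewed and MIDAS was applied to determine the baseline score". All patients then receive WCT on Days 0, 30 and 60. Randomisation follows: "At the end of the 3rd month patients were allocated into two parallel arms". The randomised contrast is stopping versus continuing: "Intervention group continued WCT whereas patients in the control group discontinued the treatment". After that, "MIDAS was applied again at the end of the 6th and 12th months to both of the groups". The comparison is described as "Disability values in the 6th and 12th months were evaluated with MIDAS between those who continued treatment (Group 1) and those who did not". No other MIDAS time point appears.

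The MIDAS section gives the recall period. Items 1, 3 and 5 "evaluate the days lost from school, work, housework or leisure activities because of headaches in the last 3 months". For the other two scored items, "The 2nd and 4th questions evaluate the number of additional days lost from work or housework in the last 3 months". The total score is the sum of these five items.

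**The concern.** The trial asks whether patients who have already had three WCT sessions do better if they continue than if they stop. The natural reference point is their disability when the arms diverge, and that is the one point at which disability is not measured. The score called baseline is a baseline for the run-in, not for the randomised contrast.

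Three things are at stake:

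- **Description.** Balance of the arms on disability at randomisation, and change from that state, cannot be shown. A later difference cannot be described as relapse after stopping or as further gain with continuing.
- **Precision.** The covariate closest in time to the outcome, taken after the treatment common to all, is likely the most predictive one, and it is not collected.
- **Reading a null result.** If the arms do not differ, it is harder to tell a run-in benefit that lasted from no initial benefit.

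The SAP was not available for this review, but the point does not depend on it. A SAP chooses covariates; it cannot supply a measurement that the schedule omits.

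**Working it through.** **Timeline.** Months are counted here from Day 0.

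| Time | Event | MIDAS | Period recalled |
|---|---|---|---|
| Entry | Baseline score | Yes | About month -3 to 0 |
| Days 0, 30, 60 | WCT for all | No | - |
| End of month 3 | Randomisation | No | - |
| End of month 6 | Follow-up | Yes | Months 3 to 6 |
| End of month 12 | Follow-up | Yes | Months 9 to 12 |

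There is one pre-randomisation score, it precedes all three sessions, and no score covers months 0 to 3. The protocol does not say whether months 6 and 12 count from Day 0 or from randomisation. If from randomisation, the follow-up windows move later and the gap stays.

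**Inputs for precision.** The protocol states no sample size, SD, effect size or correlation, so there is no figure of its own to reproduce. The following are assumptions:

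- correlation of the Day-0 score with the outcome, r0 = 0.3 to 0.5;
- correlation of a month-3 score with the outcome, r3 = 0.5 to 0.7;
- correlation between the two earlier scores, r03 = 0.4 to 0.6.

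**One covariate or the other.** Analysis of covariance leaves a residual variance proportional to 1 - r². The relative sample size is (1 - r0²)/(1 - r3²). At 0.4 and 0.6 this is 0.84/0.64 = 1.31.

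| r0 | r3 = 0.5 | r3 = 0.6 | r3 = 0.7 |
|---|---|---|---|
| 0.3 | 1.21 | 1.42 | 1.78 |
| 0.4 | 1.12 | 1.31 | 1.65 |
| 0.5 | 1.00 | 1.17 | 1.47 |

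For an assumed difference of 0.5 SD, two-sided 5% and 80% power, the central case needs 53 per arm with Day 0 and 41 with month 3 (63 unadjusted).

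**Adding month 3 to a model that already has Day 0.** R² = (r0² + r3² - 2·r0·r3·r03)/(1 - r03²), and the ratio is (1 - r0²)/(1 - R²). An analysis with 80% power on Day 0 alone would have power Φ((1.96 + 0.842)·√ratio - 1.96).

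| r0, r3, r03 | R² | Ratio | Power |
|---|---|---|---|
| 0.5, 0.5, 0.6 (minimum) | 0.20/0.64 = 0.3125 | 0.75/0.6875 = 1.09 | 83% |
| 0.4, 0.6, 0.5 (central) | 0.28/0.75 = 0.373 | 0.84/0.627 = 1.34 | 90% |
| 0.3, 0.7, 0.6 (maximum) | 0.328/0.64 = 0.5125 | 0.91/0.4875 = 1.87 | 97% |

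**Validity.** A simulation used 50 per arm (assumed), 4000 runs and the central correlations. With no true effect, mean estimates were 0.01 (Day 0) and 0.00 (month 3), and rejection rates were 0.050 and 0.055. With a true effect of -0.50 SD, both estimates averaged -0.50 and power was 0.76 and 0.86. The omission therefore costs precision, not validity.

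**Value of the Day-0 score alone.** Against no adjustment, it is worth 1/(1 - r0²): 1/0.91 = 1.10 to 1/0.75 = 1.33 times the sample size.

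**The case against.** The case against giving this weight has five parts.

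1. **Recall window.** A MIDAS taken at the end of month 3 sums lost days over the whole run-in, including the time after only one or two sessions. It is not disability at the moment of allocation. This is true and should be said when the score is reported. It does not defeat the proposal: the outcomes carry the same three-month window, and a month-3 score is the nearest pre-allocation value that the instrument can give.
2. **No stated analysis needs the score.** The protocol compares values at months 6 and 12, and randomisation makes that comparison valid without any baseline. Balance on the Day-0 score can still be shown. This stands, and it is why no bias is claimed.
3. **The null-result ambiguity comes mainly from the uncontrolled run-in.** This also stands. A month-3 score would narrow the ambiguity but not settle it.
4. **The size is assumed.** The chosen ranges never let Day 0 predict better than month 3, and one set of correlations serves both follow-up times although nearness counts for less at month 12. The figures illustrate a plausible cost and do not establish one. The descriptive loss does not depend on any correlation.
5. **The data may already be collected.** The text is in the past tense, with inclusion to January 2018. In that case only the fallback remains.

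**Conclusion.** The concern holds. It is certain from the text that no MIDAS is listed at randomisation and that no score covers the run-in. Balance on post-run-in disability and change from it therefore cannot be shown.

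The comparison of continuing with stopping at months 6 and 12 is not biased, and the Day-0 score is a valid covariate. How much precision is lost is uncertain: the equivalent of 1.00 to 1.78 times the patients when one covariate replaces the other, with 1.31 as the central case. This rests wholly on assumed correlations, and the loss may be nil. The point is worth fixing because the remedy is cheap, not because the trial's main comparison is invalid.

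**What to change.** Apply MIDAS to every patient at the end of month 3, before the envelope is opened, and name that score as the covariate for the month-6 and month-12 comparisons. Keep the Day-0 score as the pre-run-in value and, if wanted, as a second covariate. State that the month-3 score reflects the run-in period.

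The cost is one extra seven-question form per patient. The protocol describes no month-3 visit (the last listed run-in session is Day 60), so a telephone contact may be needed.

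If data collection is complete, the score cannot be recovered. Then adjust both comparisons for the Day-0 score, which needs no new data, and state as a limitation that disability at randomisation was not measured.

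### Does the protocol need to say whether the month 6 or the month 12 MIDAS comparison decides the trial?

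*Protocol*

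**What the plan says.** The Methodology section, under Study design and Patient selection, describes a three-month run-in of wet-cupping therapy (WCT) followed by randomisation: "At the end of the 3rd month patients were allocated into two parallel arms". The contrast is between continuing and stopping: "Intervention group continued WCT whereas patients in the control group discontinued the treatment". Follow-up has two assessments: "MIDAS was applied again at the end of the 6th and 12th months to both of the groups". The sentence on the comparison names both months together: "Disability values in the 6th and 12th months were evaluated with MIDAS between those who continued treatment (Group 1", and goes on to name those who stopped as Group 2.

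The MIDAS section defines the score: "The total MIDAS points are obtained from the total of the first 5 questions". It also defines four grades from that total. The items look back three months; questions 1, 3 and 5, for example, "evaluate the days lost from school, work, housework or leisure activities because of headaches in the last 3 months".

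Neither section names a primary time point, a testing order, a significance level or a rule for success. Neither says whether the arms are compared on the total or on the grade. The statistical analysis plan, where such details often sit, is not shown.

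**The concern.** Two between-arm comparisons of one outcome are named in one sentence, and nothing ranks them. A reviewer's first reaction is that a trial should say which comparison carries its conclusion, and that this is a matter of design and not only of test mechanics.

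The two months are not interchangeable. One assessment falls three months after allocation and the other nine months after, and their recall periods do not overlap. An early and a late effect of stopping WCT could therefore truly differ.

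Two things would be at stake. If the months disagreed, the protocol would not say what the trial concludes. If a difference at either month were accepted as success, the false-positive rate would exceed that of a single test.

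**Working it through.** The protocol gives no sample size, power or alpha, so it has no figure of its own to reproduce. The check asks what the silence could cost, and under which readings.

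**Inputs from the protocol**
- Randomisation at the end of month 3; assessments at the end of months 6 and 12.
- Recall of 3 months.
- Two arms: continue or stop.

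**Assumed inputs (not in the protocol)**
- Two-sided alpha of 0.05 at each month, critical value 1.960.
- Correlation between the two test statistics from 0 to 0.9.
- For the disagreement figures only: 80% power at each month and the same true effect at both.

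**Step 1: recall windows.** Month 6 covers 6 − 3 = 3 to 6. Month 12 covers 12 − 3 = 9 to 12. Both windows lie wholly after randomisation, so each is a valid period for comparing the arms.

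**Step 2: false positives if either month counts.** P(at least one) = 1 − P(|Z1| ≤ 1.960 and |Z2| ≤ 1.960), with Z1 and Z2 bivariate normal. At correlation 0 this is 1 − 0.95² = 0.0975.

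| Correlation | 0 | 0.5 | 0.7 | 0.8 | 0.9 |
|---|---|---|---|---|---|
| P(at least one false positive) | 0.0975 | 0.0907 | 0.0835 | 0.0781 | 0.0704 |

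The ratio to 0.05 runs from 0.0704/0.05 = 1.4 to 0.0975/0.05 = 1.95.

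**Step 3: disagreement under a real, equal effect.** The mean of each statistic is 1.960 + 0.842 = 2.802. P(exactly one significant) = 2 × (0.80 − P(both)).

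| Correlation | P(both) | P(exactly one) |
|---|---|---|
| 0.5 | 0.687 | 2 × 0.113 = 0.226 |
| 0.7 | 0.713 | 2 × 0.087 = 0.174 |
| 0.8 | 0.729 | 2 × 0.071 = 0.142 |
| 0.9 | 0.750 | 2 × 0.050 = 0.100 |

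These figures count any pair of p-values on opposite sides of 0.05. The true effect here is identical at both months, so such splits are chance, not conflicting answers. Naming a primary month would not make them rarer; it would only say which p-value to read. Nor do the figures measure a true difference between early and late effects, since they assume there is none.

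**Step 4: the readings that the sentence allows.**

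| Reading | False-positive rate for the trial's conclusion |
|---|---|
| Two tests, either suffices | 7.0% to 9.75% |
| Two tests, both required | at most 5% |
| One repeated-measures contrast over both months | 5% |
| Both months reported side by side, neither claimed as decisive alone | no either-month claim, so no inflation from it |

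Only the first row shows a problem, and it needs a success rule that the protocol does not contain.

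**The case for a change.** The strongest case for acting is that the choice of decisive time point differs from the choice of test or alpha. It belongs in the protocol even when the statistical analysis plan supplies the rest, and here the protocol fixes two comparisons without ranking them. One or two sentences naming a primary month, with the other tested second at the same alpha, would hold the error at 5% with no added patients. Over the correlations shown from 0.5 to 0.9, exactly one month would be significant in 10% or more of trials under the assumed power, so the situation is not remote.

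Part of this stands. The protocol does not rank the months, the recall windows do differ, and the arithmetic is right on its assumptions. A lone significant result at one month should be read with that in mind.

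The rest does not carry. Neither time point is wrong, and the protocol does not contradict itself here. The equal footing is inferred from two months sharing a sentence, which does not say that they are separate tests or that one alone would suffice. The proposed remedy is itself a testing order and a success rule, which may well be in the unseen statistical analysis plan. Month 12 or month 6 would serve equally well as primary, so the choice is a preference and not a correction. The text also reports conduct and evaluation in the past tense, with patients drawn from May 2016 to January 2018. If outcomes had been seen, a primary month named now would not be prespecified and would not hold the error at 5%. What would be left is a sentence of disclosure, which alters no result.

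**Conclusion.** No change to the plan follows. The protocol leaves unwritten which of two valid follow-up times leads, and analysts can fill that gap sensibly: estimate the difference between arms at both months, show both with their uncertainty, and do not present one month alone as the confirmatory result unless it was named in advance.

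The possible cost is a false-positive chance of about 7.0% to 9.75% in place of 5%. It arises only if the months are tested separately, each at two-sided 0.05, and either is taken as success. Alpha, the correlation range of 0 to 0.9 and the success rule are all assumptions. Under the other readings of the same sentence there is no such inflation. This conclusion would change if a document showed that a difference at either month was to count as success without adjustment.
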